4. DURATION OF PROJECT

Data collection will start since September 2019 to March 2021. Another 3 months for data management and analysis and another 3 months for report writing are required. Therefore the total duration of the project is 18-24 months. The writing and publication of scientific papers may continue after this.

5. MAIN PROBLEMS ANTICIPATED

No major problems are anticipated.

6. EXPECTED OUTCOMES AND DISSEMINATION OF THE FINDINGS

We hypothesize that the swaddling would be harmful to Graf Type 2a hips. The results will be published in national and international journals. Also a booklet with a summary of the research findings, including the recommendations, will be produced and distributed to. To make our research findings known to the participating communities, the research team will disseminate the project results through Radio/TV programmes.

7. ETHICAL CONSIDERATIONS

The study protocol will be reviewed and approved by the Institutional Review Board at the National Center for Maternal and Child Health and the Ethical Review Committee of Ministry of Health, Mongolia prior to start the study. All research data collected will be stored securely and confidentially. Strict standards of confidentiality will be observed throughout the study scheduling, administration and disposition. Participating baby will be assigned an ID number to be used during

[figure not shown]
data collection and analysis. All completed study forms will be kept in a secured, locked area under the direct supervision of the principal investigator. Following the study, the paper copies of the “Informed consent form” will be kept in a locked file cabinet in the office of the principal investigator. At no time will any participant be identified by name in any report, summary, or publication of the data. The data available for analysis will contain only a case ID number. All paper, examination and ultrasound pictures will be stored in a locked filing cabinet at the principal investigator’s office. Access to these records will be limited to staff authorized by the principal investigator to handle the documents. These records will be destroyed five years after the completion of the study.

REFERENCE

5. Lehmann H. P., Hinton R., Morello P., & Santoli J. Developmental dysplasia of the hip practice guideline: Technical report. *Pediatrics* 2000; 105(4), e57–e57. 10.1542/peds.105.4.e57.

Annex 3. Trail profile reporting

Trail profile scheme

Annex 4. Data analysis plan

Table 1. Baseline characteristics of participants

Characteristics	Non-swaddling	Swaddling	P value*
	N= n(%)	N= n(%)	
Mean age in days at screening (mean ±sd)			
Girls			
Breech position			
Family history of DDH			
Birth weight >4000			
Firstborn baby			
Mean of Graf hip alpha angle at initial screening (mean ±sd)			
Swaddling days			
Swaddling hours per day in			

sd-indicates standard deviation, *DDH* indicates Developmental Dysplasia of the Hip

**chi*² or χ^2 test

Table 2. The associations between the main outcomes and the intervention analyzed by univariate analysis (*chi*² or χ^2 test)

Characteristics	Control	Intervention	OR	P value
	n/N (%)	n/N (%)		
Mean age in days at screening				
Girls				
Breech position				
Family history of DDH				
Birth weight >4000				
Firstborn baby				
Mean of Graf hip alpha angle at initial screening				
None-Type 1 hips				
DDH				
Rim defects at follow-ups				

Table 3. The associations between the main outcomes and the intervention analyzed by multiple logistic model

	Control n/N (%)	Intervention n/N (%)	Adjusted OR*	P
Primary outcome				
None-Type 1				
Secondary outcome				
DDH				
Rim defect				

DDH indicates Developmental dysplasia of the hip, OR indicates odds ratio

**Will be adjusted for significant baseline variables*

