3.5. Statistical analysis

Data will be double computerized using EpiData (The EpiData Association Odense, Denmark) and analyzed using Stata software 9 (Stata Corporation). All ultrasound examination pictures will be uploaded to the HipScreen platform.

Balance checks for the “swaddling” and “non-swaddling” groups will be conducted and reported for all key individual-level variables measured at baseline, including age at hip ultrasound screening in days, gender, risk factors (birth weight ≥ 4000 gr, breech delivery, family DDH history, parity etc.), Graf hip type, alpha angles at baseline and management.

The primary and secondary outcomes will be described as percentage adjusted for the available baseline variables. Outcomes will be evaluated in an intent-to-treat analysis. Univariate analyses will assess factors that will be associated with outcomes and identify potential confounders (with rate ratios of ≥ 2) or variables that differed between study groups at enrollment. These covariates will be included in multivariate analyses. Multivariate logistic regression will be used to estimate the adjusted risks for prevalent outcomes. Pearson's correlation coefficient will be calculated between “non-Type 1” and swaddling days and swaddling hours per day.

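### Annex 4 names only a chi-square test for P values that cover mean age and mean alpha angle, and baseline significance is one route into the adjusted model (minor)

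*Protocol*

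**What the plan says.** Annex 4 of the protocol holds three table shells.

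- **Table 1 (baseline).** There is one P-value column, and its footnote reads "chi*² or χ^2 test". The rows under it include "Mean age in days at screening (mean ±sd" and "Mean of Graf hip alpha angle at initial screening (mean ±sd", along with swaddling days and swaddling hours. The other rows are yes/no characteristics.
- **Table 2.** The title, "The associations between the main outcomes and the intervention analyzed by univariate analysis", carries the same test wording in brackets. Mean age and mean alpha angle appear again, under columns for n/N (%), OR and P.
- **Table 3 (multiple logistic model).** The footnote says of the odds ratio: "Will be adjusted for significant baseline variables". It names neither a test nor a level.

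Section 3.5 lists "Graf hip type, alpha angles at baseline and management" among the variables to be checked for balance. It selects covariates by univariate analyses that "identify potential confounders (with rate ratios of ≥ 2) or variables that differed between study groups at enrollment", and an earlier sentence there speaks of adjusting outcomes for whatever baseline variables are available. The methods it names are logistic regression ("Multivariate logistic regression will be used to estimate the adjusted risks for prevalent outcomes") and Pearson's correlation. The protocol mentions no t-test or rank test anywhere.

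**The concern.** A chi-square test compares counts in categories. To use it on alpha angle, someone must first cut the angle at a threshold or cross-tabulate it degree by degree. The protocol fixes neither, and the two give different P values. In Table 2 a mean has no n/N, and an odds ratio for it needs a unit and a named outcome; neither is given.

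This would be a matter of presentation if baseline P values had no further use. Here they can have one. Table 3 adjusts for significant baseline variables, and Section 3.5 admits variables that differ between groups at enrolment. Alpha angle is likely to matter for the outcome. Section 3.4 defines Type 2a hips as 50 to 59° and assumes maturation of 1° per week, so on the protocol's own figures a 1° imbalance is worth about one week of maturation. Whether the adjusted odds ratio accounts for it could therefore turn on an unstated choice of tabulation.

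**Working it through.** **Stated figures.** The protocol gives no figure on this point. The only design number needed is the group size. Section 3.2 calculates 7.9 × (0.1 × 0.9 + 0.4 × 0.6) / 0.3² = 7.9 × 0.33 / 0.09 = 28.97, rounded up to 29. Allowing for 20% dropout gives 29 / 0.8 = 36.25, so 37, which fits the planned figure of about 40 per group. The check uses n = 40.

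**Inputs**

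- n = 40 per arm, 1:1 (Section 3.2)
- alpha angle in whole degrees, limited to 50–59 (range from Section 3.4; whole degrees assumed)
- two-sided 5% level (from the sample-size text; Table 3 gives none)
- SD of 2 to 2.5° and mean of 56° in one arm: **assumptions**, not in the protocol

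**Step 1: how much the test matters.** Angles were drawn from normal distributions with means 56 and 56 − d, rounded and clipped to 50–59, in 4,000 trials per setting. Each trial was tested in three ways. The figures are the share of trials with P < 0.05. Clipping makes the realised difference slightly smaller than d.

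| d | SD | t-test | chi-square, median split | chi-square, by degree |
|---|---|---|---|---|
| 0 | 2 | 4.4% | 5.5% | 3.7% |
| 0 | 2.5 | 4.8% | 5.2% | 3.8% |
| 1° | 2 | 59% | 42% | 21% |
| 1° | 2.5 | 40% | 29% | 13% |
| 1.5° | 2 | 91% | 75% | 48% |
| 1.5° | 2.5 | 76% | 57% | 31% |

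Both forms of chi-square flag a difference less often than the t-test. The loss is moderate with a median split and large by degree.

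**Step 2: how often such a difference arises.** Under sound randomisation the difference is chance. Its standard error is SD × √(2/40).

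- SD 2: 2 × 0.2236 = 0.447°; 1 / 0.447 = 2.24; two-sided probability of 1° or more about 2.5%.
- SD 2.5: 2.5 × 0.2236 = 0.559°; 1 / 0.559 = 1.79; probability about 7.4%.

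**Step 3: whether the baseline P value is the only way in.** Table 3 says significant, without naming a test. Section 3.5 says either a group difference or a rate ratio of at least 2. The second route does not use the Table 1 P value. It is not a dependable one for alpha angle, though. A rate ratio for a continuous variable needs a cut-point or a unit, and neither is given. If a larger angle lowers the risk, the ratio per degree is below 1 and fails the criterion as written.

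**The case against.** The strongest reply has four parts.

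1. **The doubled wording may be a slip.** A footnote of the form A or B normally names two tests, and the second may have been mistyped or lost when the PDF was read. The text cannot settle this, so the point is that the wording must be corrected, not that a chi-square on means was deliberately chosen. Even if a t-test was meant, Table 2 still puts means under counts and odds ratios.
2. **Naming tests is work for a SAP.** Silence would indeed be no finding. But Annex 4 is headed as the data analysis plan and does name a test, which does not suit these rows.
3. **The consequence is limited.** A reader might infer that the chi-square result decides what Table 3 adjusts for, and so leaves the primary odds ratio unadjusted. The documents do not support that. The Table 3 footnote does not tie significance to the Table 1 test, and Section 3.5 has a second route. This part of the reply stands.
4. **A 1° imbalance is rare, and the by-degree table is the worst case.** Both are true. A reader might infer from the by-degree figures that a real imbalance would usually be missed, but the protocol does not propose that tabulation and the median split loses much less. The rarity argument assumes that only chance creates imbalance. Section 3.3 places written consent after randomisation, so selective refusal could also contribute.

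**Conclusion.** The point holds as a minor one. As printed, the only test named for the P values of Tables 1 and 2 does not suit their mean rows, and the Table 2 columns cannot hold those rows. This follows from the text and needs no assumption.

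The effect is on covariate selection. The test is one route, not the only one, by which alpha angle enters or is left out of the adjusted odds ratio. The size of the loss rests on the assumed SD and on a tabulation that the protocol does not state, and a chance difference of 1° or more is uncommon. A reader might go further and doubt the primary comparison itself. That is not supported: the primary outcome is binary, chi-square suits its unadjusted comparison, and the sample size is untouched.

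**What to change.** 1. **Table 1.** Name a two-sample t-test or Wilcoxon rank-sum test for the quantitative rows: age, alpha angle, and swaddling days and hours if these are tested. Keep chi-square for the yes/no rows, with Fisher's exact test where cells are sparse.
2. **Table 2.** Show mean (sd) for age and alpha angle. Give their odds ratios from univariate logistic regression, per day and per degree, and state the outcome (non-Type 1 for the primary).
3. **Table 3 and Section 3.5.** Reconcile the two selection rules, preferably by prespecifying baseline alpha angle as a covariate. Changing the test alone would not be enough: with a 1° difference even the t-test is non-significant in about 41–60% of trials (100% minus 59% and 40%). Prespecification means that adjustment for alpha angle no longer depends on a baseline P value.

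The cost is a few lines of table and footnote text. No new data are needed, and the sample size and primary comparison stay as they are.

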TRADITIONAL MONGOLIAN SWADDLING AND DEVELOPMENTAL DYSPLASIA OF THE HIP: A RANDOMIZED CONTROLLED TRIAL

RESEARCH PROTOCOL

[name] and SMOPP team
National Center for Maternal and Child Health, Mongolia
29 June, 2019

SUMMARY

Background

In Mongolia, swaddling is an ancient practice and nowadays it still remains common child care in the first months of life. Mongolian traditional way of swaddling technique involves tight, prolonged wrapping from the head or neck down in two to three layers of thin cotton cloth, covered by layers of thick blankets and binding with 2-3 tiers for whole day. This traditional prolonged swaddling where arms and legs are extended and hips are in adduction position might increase the risk for developmental dysplasia of the hip (DDH). DDH is a major health problem that can lead to lifelong disability if diagnosis is missed in first weeks of life. Mongolia is the first Asian country that launched a universal ultrasound hip screening (Graf's method) for DDH in newborns. All DDH cases are followed up on monthly basis by hip ultrasound and treated with a simple extension and abduction orthosis if necessary.

Objectives

To test the effect of traditional swaddling on the DDH in Mongolia

Design

A prospective, randomized trial with two study groups will be conducted in Mongolia. The term newborns with Graf Type 2a (physiologically immature) will be randomly allocated to one of two groups. The intervention/"non-swaddling" group will be instructed not to swaddle at all. The control/"swaddling group" will be swaddled in the common traditional Mongolian method. Both groups will be followed up by Graf's method of hip ultrasound at 4-6 weeks' intervals until healing according to Mongolian national guideline. All infants in need of therapy (Graf type 2a-, 2c or worse) will be treated with Tubinger orthosis. At around 12 months of age all children will be checked again by Graf's method of hip ultrasound.

Timeline and Analysis

The study will be conducted between August 2019-March 2021. Findings will be reported in March-June 2021. Analysis will be intention to treat.

Ethics

The study protocol will be reviewed and approved by the Institutional Review Board at the National Center for Maternal and Child Health and the Ethical Review Committee of Ministry of Health, Mongolia prior to start the study.

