2. OBJECTIVES

Mongolian traditional prolonged swaddling where arms and legs are extended and hips are in adduction position increases the risk for DDH. This hypothesis is going to be tested in this study.

The primary outcomes: The number of “non-Type 1” hip cases at the monthly follow-up ultrasound control visits

The secondary outcomes:

- a. number of DDH cases (Graf Type 2a-, Type C, D and Type 4) at any monthly follow-up ultrasound control visits and rim defects at 12 months’ follow-up
- b. correlation between the primary outcome and the swaddling frequency (in hours per day) and swaddling duration (in days)
- c. primary and secondary outcomes association with the swaddling.

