For babies assigned to the “swaddling” group, parents will be instructed to follow a pattern of traditional Mongolian swaddling as described above. For babies assigned to the “non-swaddling” group, parents will be instructed to do not swaddle at all and only use a wide sleeping bag with free leg position.

Trained research assistants will make home visits on weekly basis until the infants are 4-6 weeks of age to check and monitor the compliance of the families by observing the baby during every home visit and collecting retrospectively 24-hour diaries of swaddling and non-swaddling patterns. Also unscheduled visits from monitoring research assistants will be organized to estimate unreported non-compliance conducted for all families 2 to 3 times.

At 4-6 weeks follow up visit, the babies will be checked by Graf’s method of hip ultrasound performed by a trained radiologist uninformed about the initial status of the hips. Regardless of the study group, monthly controls will be fixed until complete maturation to Graf type 1 is documented. Families, who did not show up for follow-up will be contacted by phone or home

visit. In cases when the parents will not be able/willing to come to the follow-up control visit(s), the PI will visit the family and make the follow-up ultrasound examination at their home using a portable ultrasound device (MicroUs EXT-1H, REV:C). All infants in need of therapy (Graf type 2a-, 2c or worse) will be treated with Tubinger orthosis.

Monitoring: In the non-swaddling group, it is expected that some families would not adhere to their instructions of not swaddling because of grandparents/cultural pressures. To monitor compliance and obtain a measure of exposure, multiple sources of information will be used:

1. A retrospective 24-hour history of swaddling/clothing: will be recorded by research assistants during each weekly home visit through recording the carer's descriptions of the style of dress/clothing/ swaddling and length of each during the past 24-hour within the 24-hour retrospective diaries (a kind of behaviour diary adapted to record swaddling/clothing pattern)
2. Direct observation of research assistants during weekly visits: of the dressing/clothing/ swaddling of each child and discreetly recording observations of the type of baby clothing items that each family washed and hung to dry on the day of visit (available for observation during the majority of visits)

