3.4. Outcome assessments

The primary outcome of the study will be the number of “non-Type 1” hip cases at the any monthly follow-up ultrasound control visits.

The secondary outcomes are:

- a. number of DDH cases (Graf Type 2a-, Type C, D and Type 4) at any monthly follow-up ultrasound control visits
- b. correlation between the primary outcome and the swaddling frequency (in hours) per day and swaddling duration in days
- c. primary and secondary outcomes association with the swaddling.

Operational definitions

Swaddled: Newborns are swaddled in the common traditional Mongolian method at least 20 hours per day for 4-6 weeks

Non swaddled: Newborns are not swaddled at all.

The “non-Type 1” hip case: a neonate who’s Graf ultrasound type is other than Type 1 at any monthly follow-up visits

Physiologically immature or Graf Type 2a hip: has a certain degree of physiological delay in ossification of the bony acetabular roof. The alpha angle is between 50 and 59, the beta angle is between 55 and 77, and the patient is younger than 6 weeks of age.

Graf Types 2a- and 2a+: Starting from 55° alpha at 6 weeks of age and assuming a spontaneous maturation of 1° per week. Type 2a+ is still considered to be physiological while 2a- hips are assigned to the group of DDH.

Swaddling hours: according to the 24-hour diaries of swaddling and non-swaddling patterns of mothers and research assistants' compliance check reports

Swaddling days: according to the 24-hour diaries of swaddling and non-swaddling patterns of mothers and research assistants' compliance check reports

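### The rim-defect secondary outcome is set at 12 months in section 2, omitted from section 3.4, and given no fixed visit in the Annex 4 tables

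*Protocol*

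**What the plan says.** Four parts of the protocol bear on this outcome.

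- **Section 2, secondary outcome a.** DDH and rim defects share one line but have different timing: DDH is counted "at any monthly follow-up ultrasound control visits and rim defects at 12 months". DDH is thus an any-visit outcome and rim defect a single-visit one.
- **Section 3.4, secondary outcome a.** The list is repeated as "number of DDH cases (Graf Type 2a-, Type C, D and Type 4) at any monthly follow-up ultrasound control visits" and ends there. Rim defects are not mentioned, and the operational definitions in the same section do not cover them.
- **Annex 4, the data analysis plan.** Table 2 has the row "Rim defects at follow-ups". Table 3 lists rim defect under secondary outcomes with no time point.
- **Scan schedule.** The Summary plans one late scan for everyone: "At around 12 months of age all children will be checked again by Graf's method of hip ultrasound". Section 3.3 describes the earlier scans: all infants are scanned at 4-6 weeks, and then "monthly controls will be fixed until complete maturation to Graf type 1 is documented".

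**The concern.** A single scan offered to every child and a count over all follow-up scans give different event sets. With the outcome absent from section 3.4, an analyst filling in Table 2 has no text that decides between them, and the choice could be made after the results are known.

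The two readings also differ in how fairly they compare the arms. The 12-month scan is planned for all children. The number of monthly scans depends on how quickly a hip reaches Type 1, which is what the trial expects swaddling to change. An any-visit count would give the slower-maturing arm more occasions on which a finding can be recorded. It would also pool findings from the first weeks with findings at 12 months, although some infants will have had orthosis treatment in between.

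**Working it through.** **1. The places side by side.**

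| Place | Rim defect listed? | Time point |
|---|---|---|
| Section 2 | yes, secondary | 12-month follow-up |
| Section 3.4 | no | none |
| Annex 4 Table 2 | yes | follow-ups, plural, no visit named |
| Annex 4 Table 3 | yes, secondary | none |

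The 12-month scan appears only in the Summary and section 2. The non-Type 1 and DDH rows of the tables also lack a time point, but section 3.4 supplies one for each of them. For rim defect it supplies nothing, and Table 2 adds a time phrase that differs from section 2.

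**2. The plan's own figure.** The only calculation in the protocol is for the primary outcome (section 3.2): 7.9 × [0.1 × 0.9 + 0.4 × 0.6] / 0.3² = 7.9 × 0.33 / 0.09 = 28.97, so 29 per group. This reproduces, and it does not depend on how rim defects are counted. No rate or power is given for rim defects.

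**3. Who gets extra scans.** Inputs are 10% and 40% non-Type 1 and about 40 infants per group with 20% dropout (section 3.2), and the stopping of monthly scans at Type 1 (section 3.3). Because scanning stops at Type 1, an infant who is non-Type 1 at any monthly visit was already non-Type 1 at the first one, and so goes on to at least one more scan.

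- With 40 per arm: 0.10 × 40 = 4 against 0.40 × 40 = 16 infants.
- With 40 × 0.8 = 32 per arm: 3.2 against 12.8.

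The ratio is four. It holds whatever a rim defect turns out to be.

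**4. What unequal scanning alone might do (illustration only).** Assume that each scan has a 5% chance q of recording a finding, independent of arm, hip type and other scans. Assume also that every infant has two scans (4-6 weeks and 12 months) and that non-Type 1 infants, a proportion p, have k extra. The any-visit rate is 1 − (1 − q)² × [(1 − p) + p(1 − q)^k].

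- k = 1: 1 − 0.9025 × 0.995 = 10.2% against 1 − 0.9025 × 0.98 = 11.6%; odds ratio 1.15.
- k = 3: 1 − 0.9025 × 0.9857 = 11.0% against 1 − 0.9025 × 0.9430 = 14.9%; odds ratio 1.41.
- 12-month scan only: 5% in both arms; odds ratio 1.

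The values of q and k are assumptions, not figures from the protocol.

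**5. What mixing in early findings might do (illustration only).** Assume a 12-month rate of 5% in both arms, and that a fraction f of the hips that are non-Type 1 at the first follow-up scan is recorded as a rim defect. The any-visit rate is 1 − 0.95 × (1 − p × f), with p = 0.10 or 0.40.

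| f | Non-swaddled | Swaddled | Odds ratio |
|---|---|---|---|
| 0 | 5.0% | 5.0% | 1.0 |
| 0.1 | 6.0% | 8.8% | 1.5 |
| 0.25 | 7.4% | 14.5% | 2.1 |
| 0.5 | 9.8% | 24.0% | 2.9 |
| 1 | 14.5% | 43.0% | 4.4 |

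This is not a measure of unequal scanning: it uses the 4-6 week scan, which both arms receive. Everything turns on f, about which the protocol says nothing.

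**The case against.** The strongest reply is that this is a loose row label. Section 2 itself calls the 12-month check a follow-up, so the Table 2 wording may be shorthand for it. Where the authors mean any visit they say so expressly, and Table 2 does not. The annex is a table shell that leans on the body text throughout. This has weight: the any-visit reading is possible but not certain. It does not remove the inconsistency. The protocol plans one 12-month scan, so a plural without a visit does not identify it, and section 3.4, where a reader would look for the answer, is silent.

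A reader might infer more: that an early rim defect is simply the immature roof of a Type 2a hip, so that the row would count normal immaturity and largely repeat the primary result. The documents do not support this. The phrase "has a certain degree of physiological delay in ossification of the bony acetabular roof" defines Graf Type 2a, not rim defect, and the protocol never equates the two. It lists rim defect separately from both non-Type 1 hips and DDH, which suggests a distinct finding. The primary outcome is any hip whose "Graf ultrasound type is other than Type 1 at any monthly follow-up visits". A rim-defect count would come close to repeating it only if f were near 1, and nothing in the protocol shows that.

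It can also be said that an early difference between randomised arms would be a real effect on the early hip. That is right, provided the scans are equal and the result is labelled as early. It does not make such a finding the 12-month outcome named in section 2.

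**Conclusion.** The inconsistency stands: one secondary outcome has a 12-month time point in section 2, no entry in section 3.4, and no fixed visit in either analysis table. If Table 2 is filled in as titled, findings from different ages could be pooled, and about four times as many swaddled as non-swaddled infants would have further monthly scans (16 against 4 of 40). That ratio rests on the protocol's own assumed rates of 40% and 10%.

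The effect on the rim-defect comparison cannot be computed from the document, because it gives neither a definition nor a rate. The odds ratios above show only what stated assumptions would imply, from none at f = 0 to large at f = 1, and should not be quoted as the expected bias. Severity is minor: the outcome is secondary, and the primary comparison and the sample size are unaffected.

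**What to change.** - In Annex 4 Tables 2 and 3, label both rows *Rim defect at the 12-month scan*.
- Use as denominator the number scanned at 12 months, shown by randomised arm. This keeps infants in the arm to which they were allocated, in line with the intention-to-treat statement in section 3.5, and makes missing 12-month scans visible.
- State that findings at earlier scans are not counted as events for this outcome.
- Restore rim defect to the secondary outcomes in section 3.4 with the same time point, and add one definition, to be supplied by the investigators, to the operational definitions.

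The cost is a few lines of wording. The 12-month scan is already planned for all children, so no new examination is needed. The downside is possibly fewer events than an any-visit count, and hence a less precise estimate.
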